The study will be carried out in accordance with this protocol, the guidelines and ethical principles set forth in the Declaration of Helsinki, Good Clinical Practice (ICH-GCP) and SA GCP. Any proposed changes to this protocol, or to informed consent or participant information documents, will be submitted to the Human Research Ethics Committee of the University of Cape Town for approval prior to implementation. Monitoring representatives of the South African Health Products Regulatory Authority (SAHPRA), or representatives of the Human Research Ethics Committee of the University of Cape Town, South Africa will have reasonable access to inspect facilities and study records at the study site.

PBMC peripheral blood mononuclear cell(s)

PCR polymerase chain reaction

PHA phytohemagglutinin

PID participant identification number

POI prevention of infection PT prothrombin time

PTT partial thromboplastin time

QFT QuantiFERON®-TB
SAE serious adverse event
SAER Supplemental SAE Report

SAHPRA South African Health Products Regulatory Authority

SATVI South African Tuberculosis Vaccine Initiative

SOP Standard Operating Procedure

SUSAR suspected unexpected serious adverse reaction

SSAR Standard Safety Analysis Report

TB tuberculosis

TBVI TuBerculosis Vaccine Initiative

TCD Triclinium Clinical Development (Pty) Ltd

TCD RA Triclinium Regulatory Department

TNF tumor necrosis factor
TSC Trial Steering Committee
ULN upper limit of normal

US United States
WB whole blood
WBC white blood cell

WHO World Health Organization

PROTOCOL SUMMARY

Title: A Phase 2a Randomised Controlled Dose-defining Trial of the

Safety and Immunogenicity of MTBVAC in healthy, BCG naïve,

HIV unexposed, South African newborns

Phase: 2a

Population: Ninety-nine HIV unexposed, BCG naïve, newborns without

known household exposure to M. tuberculosis

Number of Sites: One site in South Africa:

South African Tuberculosis Vaccine Initiative (SATVI)

Brewelskloof Hospital

Worcester South Africa

Study Duration: The estimated study duration (first participant vaccinated to

completion of data collection) is approximately 36 months.

Study Participation

Duration:

365 days

Description of Agent or

Intervention:

MTBVAC at three dose levels: 2.5 x 10⁴ CFU, 2.5 x 10⁵ CFU and 2.5 x 10⁶ CFU. The active control is BCG vaccine. Participants will receive a single dose of MTBVAC or BCG administered intradermally on Study Day 0.

Objectives: Primary:

- To evaluate safety and reactogenicity of MTBVAC at escalating dose levels compared to BCG vaccine in healthy, BCG naïve, HIV unexposed, South African newborns
- To evaluate the immunogenicity of MTBVAC at escalating dose levels compared to BCG vaccine in healthy, BCG naïve, HIV unexposed, South African newborns

Secondary:

 To evaluate QFT conversion rates in neonates receiving escalating dose levels of MTBVAC

Future exploratory:

Samples will be kept for future analyses:

 To evaluate exploratory immune responses to escalating dose levels of MTBVAC and to BCG (including, but not necessarily

limited to, analysis of innate response cytokines, specific IgG antibody responses, donor-unrestricted T-cell responses).

 To differentiate vaccine-induced immune responses from natural Mtb infection.

[figure not shown]
Design:

Double-blind, randomised, active BCG control, MTBVAC dose-finding trial with 3 cohorts of healthy, BCG naïve, HIV unexposed, South African newborns (24 BCG; 75 MTBVAC)

Estimated Time to Complete Enrollment:

The estimated time to complete enrollment is approximately 9 months.

Schematic of Study Design:

¹ Cohort 1: n=25 MTBVAC (2.5 x 104 CFU) and n=8 BCG

² Cohort 2: n=25 MTBVAC (2.5 x 10⁵ CFU) and n=8 BCG

³ Cohort 3: n=25 MTBVAC (2.5 x 106 CFU OR 2.5 x 105 CFU (n=13) plus 2.5 x 104 CFU (n=12)) and n=8 BCG

⁴ At each DSMB, all available safety data from previous cohorts enrolled will be reviewed. If any of the safety criteria is not met for the 2.5 x 10° CFU dose for Cohort 3, Cohorts 1 and 2 will be expanded so that 33 additional neonates will be randomly allocated to receive the 2.5 x 10° CFU dose (n=13), the 2.5 x 10° CFU dose (n=12) or BCG (n=8) by default.

3 BACKGROUND INFORMATION AND SCIENTIFIC RATIONALE

3.1 Background Information

A new effective tuberculosis (TB) vaccine is essential to achieve World Health Organization (WHO) End TB goals and ultimately to eliminate TB by 2050 (1). Bacille Calmette Guerin (BCG), currently the only licensed vaccine against TB, protects against disseminated TB (miliary and meningitic disease) in children, but provides inconsistent protection against the predominant form of pulmonary TB in all age groups. A new improved TB vaccine is needed that is effective against all forms of TB disease in infants, children, and adults; and safe in immune-compromised persons, including those with HIV infection. One potential vaccination approach targets adults, the drivers of the TB epidemic, to prevent transmission within the community including to susceptible children. Modeling shows that a moderately effective adult TB vaccine would be the single best tool to achieve TB elimination by 2050 (2). However, the optimal strategy would be to combine serial mass campaigns in adults, and universal newborn vaccination to provide direct protection to susceptible children who experience a high incidence rate of TB infection. Implementation of this strategy will require demonstration of safety, immunogenicity, and efficacy of a new TB vaccine in both newborns and adults.

The most robust evidence for vaccine-induced protection against TB disease in humans comes from children who received a live attenuated mycobacterial vaccine – BCG, a live-attenuated *Mycobacterium bovis* originally isolated from cattle. Systematic review suggests that BCG confers variable protection against TB disease in infants and school-age children, provided that they have not already been infected with *Mycobacterium tuberculosis* (or potentially exposed to other non-tuberculous mycobacteria) (3). However, the majority of adults in countries with high TB endemicity are latently infected (4). Therefore, although a new effective adult vaccine would be highly desirable to prevent active TB disease and halt TB transmission, adults might be the most difficult population to protect. Newborn infants are the only human population without prior mycobacterial exposure in TB endemic countries. Therefore, parallel clinical developments of MTBVAC are crucial to provide safety, immunogenicity and efficacy data in *M. tuberculosis* naïve and *M. tuberculosis* exposed populations, in order to deliver an effective, long-term TB vaccine strategy for both adults and newborns.

3.2 Rationale

BCG lacks >100 genes when compared to the human TB pathogen *M. tuberculosis* (5), that are thought to be pathogen-beneficial for the successful interaction of *M. tuberculosis* with the human immune system (6,7). Therefore, it is hypothesized that a successful vaccine against TB should incorporate several of these *M. tuberculosis* genes. Within European TB vaccine projects and TBVI, [name] (Unizar) and [name] (Pasteur Institute, France) genetically engineered a uniquely attenuated strain, MTBVAC, based on a *M. tuberculosis* clinical isolate of the Euro-American lineage (8), the most widespread and

commonly transmitted lineage between humans by the aerosol route (9). The attenuation of MTBVAC is based on two independent, stable genetic deletions of two major virulence factors in M. tuberculosis: phoP coding for the transcription factor PhoP and fadD26 coding for the synthesis of PDIM (8.10.11). MTBVAC contains most of the genes deleted from BCG and presents a wider collection of mycobacterial antigens to the host immune system. Liveattenuated strategies are also considered the best approach for conferring durable T-cell immune responses (12). It is our hypothesis that, as a live attenuated *M. tuberculosis*, MTBVAC provides a more durable T-cell response to a wider collection of mycobacterial antigens and confers improved protection compared to BCG. The Spanish vaccine manufacturer Biofabri has produced and characterized live-attenuated MTBVAC as a freezedried preparation in compliance with GMP, WHO, EMA and FDA recommendations to assure the quality, safety and efficacy of BCG vaccines. The final freeze-dried MTBVAC product has shown a robust safety, biodistribution and persistence profile comparable to licensed BCG; fulfills regulatory requirements; and has shown promising immunogenicity and protective efficacy in relevant animal models (8). Recent studies in newborn mice show that MTBVAC is safe, does not affect growth and organ development and, notably, confers superior immunogenicity and efficacy against pulmonary forms of TB, compared to BCG (13).

MTBVAC entered a first-in-human Phase 1a trial in 2012. Safety and immunogenicity of three escalating dose levels of MTBVAC (5 x 10³, 5 x 10⁴, 5 x 10⁵ CFU) was evaluated in comparison with BCG SSI in healthy Swiss adults without history of BCG vaccination or exposure to TB or HIV (14). Vaccination with MTBVAC demonstrated an excellent safety profile, comparable to BCG. MTBVAC was at least as immunogenic as BCG; and at the same dose level as BCG, the MTBVAC group showed greater frequency of polyfunctional CD4+ central memory T-cells. A transient increase in CFP-10-specific ELISPOT positivity was observed at day 28 in three adult participants who received MTBVAC (14).

Based on these promising first-in-human data, a Phase 1b evaluation of MTBVAC in healthy newborns started in 2015 at the SATVI site in South Africa (ClinicalTrials.gov NCT02729571). This trial evaluated safety and immunogenicity of three escalating dose levels of MTBVAC (2.5×10^3 , 2.5×10^4 , 2.5×10^5 CFU) for the first time in BCG naïve newborns in a TB endemic region. Twenty-eight infants received MTBVAC (9 in each of the first two dose groups, and 10 in the third), preceded by a pilot safety group of adults, previously BCG-vaccinated at birth, who received MTBVAC (2.5×10^5 CFU). Vaccination of both adults and newborns was completed without any significant safety signal. Immunogenicity results indicate that one dose of MTBVAC 2.5×10^4 or 2.5×10^5 CFU given within 96 hours of birth induced substantial cytokine-expressing (IFN- γ , IL-2, or TNF- α) antigen-specific CD4 T-cell responses that persisted for six months until the final study day. MTBVAC 2.5×10^5 CFU dose evoked the greatest magnitude response at day 70 post vaccination, whereas the lowest MTBVAC dose of 2.5×10^3 CFU was less immunogenic and did not induce a durable response at day 180. Vaccination with MTBVAC at 2.5×10^4 or 2.5×10^5 CFU is immunogenic in neonates from a TB endemic setting.

Data from this Phase 1b infant trial indicates that MTBVAC vaccination may cause interferon gamma release assay (IGRA) conversion in infants, unrelated to natural *M. tuberculosis* infection. This phenomenon is analogous to the known effect of BCG vaccination on tuberculin

skin test (TST) conversion. Three of 8 (37,5%), six of 8 (75%) and 7 of 9 (77,8%) infants who received MTBVAC at 2.5 x 10³, 2.5 x 10⁴ and 2.5 x 10⁵ dose respectively, demonstrated a positive QuantiFERON (QFT) test 180 days after MTBVAC administration, in the absence of known exposure to TB, compared to none of seven BCG recipients. At one year of age none of 8 (0%), two of 8 (25%) and 4 of 9 (44%) infants who received MTBVAC at 2.5 x 10³, 2.5 x 10⁴ and 2.5 x 10⁵ dose respectively, demonstrated a positive QFT result. This new data offers a strong indication of the immunogenicity of MTBVAC in newborns, which requires confirmation in a larger study. Further, since QFT conversion is used as a tool to diagnose *M. tuberculosis* infection in adults and older children, and as an endpoint in exploratory prevention of *M. tuberculosis* infection (POI) vaccine trials, it is critical that the mechanism of MTBVAC-induced QFT conversion and reversion is fully explored. If MTBVAC is shown to be efficacious against TB disease, these data will be important for development of alternative interferongamma release assays (IGRA) for *M. tuberculosis* infection that are not cross-reactive with MTBVAC.

Biofabri, industrial manufacturer and exclusive licensee of MTBVAC, together with intellectual property owner Unizar, has set two independent clinical development pathways for MTBVAC. One pathway focuses on development of MTBVAC for prevention of TB disease in previously BCG vaccinated adults. This clinical trial is based on the clinical development pathway of MTBVAC as a preventive pediatric vaccine that could potentially replace newborn BCG vaccination. A Phase 2a dose-defining study is a pre-requisite for selecting optimal dose for future efficacy trials of MTBVAC in newborns in TB endemic countries.

Reflecting the clinical strategy to move straight from the Phase IIa to Phase III study with a single selected dose, the design of the proposed Phase III incorporates three case-driven assessments for futility and efficacy. Such a pathway for the MTBVAC clinical development would allow for the neonatal vaccine to be made available sooner (estimated 5 years) with the potential to offer a greater magnitude of protection compared to current BCG vaccine. Such a saving in time would have a major public health benefit when considering that the BCG vaccine has been reported to have variable protective effect depending on the form of TB and the geographical location. The impact of TB in children is significant: in 2019, over one million (1 190 000) children globally became ill with TB and 230 000 died from the illness and therefore it is prudent to develop a more effective vaccine as soon as possible, within safety and regulatory requirements.

3.3 Potential Risks and Benefits

3.3.1 Potential Risks

The safety profile of MTBVAC at the highest dose to be tested (2.5 x 10⁶ CFU) is not yet known in infants. Therefore, vaccination of newborns will be staggered to allow gradual evaluation of safety and reactogenicity at each escalation of MTBVAC dose. Progression from the 2.5 x10⁵ to the 2.5 x10⁶ CFU dose level, for which safety in infants has not yet been demonstrated, will require that all of the following criteria have been met: (1) no pre-defined pausing rules have been observed at lower MTBVAC dose levels in this trial; (2) favourable review of day 28

safety data of all lower MTBVAC dose groups by the Data Safety Monitoring Board (DSMB); (3) favourable review of safety data from the current pilot Phase 1b infant trial by the DSMB; and (4) favourable review of day 28 safety data for the 2.5 x 10⁶ CFU dose level in QFT negative adults in the parallel adult trial by the DSMB. In the event that any one of these safety criteria are not met, Cohorts 1 and 2 will be expanded so that 33 additional neonates will randomly allocated to receive the 2.5 x 10⁴ CFU dose (n=12), the 2.5 x 10⁵ CFU dose (n=13) or BCG (n=8) by default. If there is a delay in adult data, dose escalation in infants will either be delayed, or Cohorts 1 and 2 be expanded as mentioned above.

MTBVAC Data Safety Monitoring Board Charter has been created as a guidance.

It is not yet known whether MTBVAC offers equivalent, better, or worse protection against TB compared to BCG. Therefore, measures to minimize risk of TB will be put in place throughout the study and, after completion of all Study D365 visits in each cohort and unblinding of the clinical team, 'catch up' BCG vaccination will be given to all MTBVAC vaccinated infants once the last participant of each cohort has performed the D365 visit, provided that the individual recipients have a negative screen for active TB disease and new household contacts, and do not have a new positive QFT result at D365. Risk of incident TB disease will be minimized by exclusion of infants with known TB exposure, including prior maternal or family history. Newborns born to HIV infected mothers, with increased risk of TB, will not be enrolled. All infants will be screened actively for TB symptoms at each study visit to diagnose TB disease early and pre-empt severe morbidity. Infants diagnosed with TB disease will remain in safety follow-up, but will be referred immediately for TB treatment, provided free of charge by health services. In the previous South African study we saw no confirmed TB cases in either adults or infants who received MTBVAC. One adult MTBVAC recipient with recent HIV seroconversion was diagnosed with aseptic meningitis and received 6 months treatment for unconfirmed TB meningitis. Two infant MTBVAC recipients (one QFT+; one QFT-) received TB treatment in the public health system for unconfirmed TB; a rate (2/28; 7%) that is similar to the rate of unconfirmed TB in a previous infant trial in this community (13% over 2 years)[29]

The QFT assay is widely used in older children and adults as a tool to aid in the diagnosis of *M. tuberculosis* infection. Given the preliminary evidence of MTBVAC vaccine induced QFT conversion in the current Phase 1b infant study, it is postulated that infants who receive MTBVAC will demonstrate QFT conversion events two months after vaccination (D56), followed by a high rate of reversion, leading to declining rates of QFT positivity at D182 and D365. The same response kinetic was observed for BCG-specific T cell responses in a prior longitudinal study in newborns (15). The observed effect of MTBVAC on QFT conversion is analogous to the known effect of BCG on false positive TST conversion; MTBVAC might be expected to have a similar effect on TST conversion.

Based on observed rates of QFT positivity 1 year after MTBVAC vaccination in infants, half or more of infants who receive MTBVAC may remain QFT positive at end of study and longer. However, it will not be possible to differentiate MTBVAC-induced QFT conversion from QFT conversion as a consequence of natural *M. tuberculosis* infection. Therefore, risk of natural *M. tuberculosis* infection will be minimized by exclusion of infants with known TB exposure, including prior maternal or family history. Infants who demonstrate QFT conversion soon after

MTBVAC administration are more likely to have converted due to vaccine effect than infants who demonstrate QFT conversion later during follow-up, who are more likely to have converted due to natural *M. tuberculosis* infection. Early (D56) post-vaccination QFT conversion in infants with low risk of natural *M. tuberculosis* exposure is assumed to be vaccine-induced and will not be treated with isoniazid preventive therapy (IPT). Infants who demonstrate early QFT conversion at D56 will undergo enhanced screening for potential new TB exposure and TB symptoms during all scheduled study visits, and in addition, during interval telephonic contacts at D120 and D270. QFT samples will be collected at D182 and D365 from infants who tested QFT positive at D56, and stored for later analysis, but since a positive QFT result would not be interpretable, these data will not be used for clinical decision-making. All infants who received MTBVAC and tested QFT positive will receive a card at the end of study indicating that they have received an experimental vaccine that may interfere with interpretation of future IGRA and TST tests for TB infection.

QFT assays will be repeated at D182 and D365 in infants who tested QFT negative at D56. These results will be made available for clinical decision-making. Infants with new QFT conversion events at D182 or D365, and any infant with a reported new household TB contact regardless of QFT status, will be referred to the public health services for IPT since these infants would potentially benefit from TB prophylaxis against *M. tuberculosis* infection as per SA national guidelines, provided that signs and symptoms of active TB disease are absent.

Known Potential Benefits

All infant participants will benefit from enhanced TB screening and facilitated referral and improved access to healthcare providers.

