5 STUDY DESIGN

This double-blind, randomized, active controlled, MTBVAC dose-finding trial will evaluate the safety, reactogenicity, immunogenicity, and potential for QFT conversion and reversion of the candidate TB vaccine MTBVAC in HIV uninfected BCG naïve newborns, administered in 3 cohorts at a single intradermal dose of 2.5×10^4 CFU (Cohort 1, n=25), 2.5×10^5 CFU (Cohort 2, n=25), and either 2.5×10^6 CFU (n=25) or 2.5×10^5 CFU (n=13) plus 2.5×10^4 CFU (n=12) (Cohort 3), compared to BCG vaccine (24 BCG; 75 MTBVAC).

Three dose levels of MTBVAC (2.5 x 10³, 2.5 x 10⁴, 2.5 x 10⁵ CFU) have been tested in the current Phase 1b trial in healthy, BCG-naïve, South African newborns; and four dose levels (5 \times 10³, 5 x 10⁴, 5 x10⁵, and 5 x 10⁶ CFU) are being tested in a parallel trial among M. tuberculosis infected and uninfected South African adults. It is our hypothesis that the optimal safe and immunogenic MTBVAC dose for infants lies in the range of 2.5 x 104 (10-fold lower than BCG) to 2.5 x 10⁶ CFU (10-fold higher than BCG). Therefore, this proposed infant trial aims to define the MTBVAC dose-response curve above and below the optimal MTBVAC dose, straddling a 3-log dose range. Final selection of the MTBVAC dose for use in the 3rd cohort will be data driven, based upon the most recent safety and immunogenicity data from all ongoing and completed trials of MTBVAC in infants and adults at that time. Infant safety data are not yet available for the highest (2.5 x 10⁶ CFU) MTBVAC dose. Therefore, selection of the 2.5 x 106 CFU MTBVAC dose would be contingent upon demonstration of an acceptable safety profile (as defined in Section 3.3.1), both for all lower MTBVAC doses in infants, and for the 5 x 10⁶ CFU MTBVAC dose in QFT negative adults (data expected end 2018/beginning 2019). If these safety criteria for the highest MTBVAC dose are not fulfilled, the 2.5 x 10⁵ CFU and 2.5 x 104 CFU MTBVAC doses would be selected for the last cohort, as described in Section 3.3.1. This approach will build upon data from the current infant pilot study and should allow detailed comparison of safety and immunogenicity of the postulated optimal MTBVAC dose within a 3-log dose range, in a larger infant study population. Refer to Figure 5-1.

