6.3 Treatment Assignment Procedures

6.3.1 Randomization Procedures

Participants will be randomized using a pre-prepared block randomization schedule, linked to study enrolment number.

Ninety-nine (99) infant participants will be recruited, randomized and allocated into 3 groups: BCG (single dose level 2.5 x 10^5 CFU/0.05 mL, n=24); or MTBVAC at three different dose levels as a single intradermal dose of 2.5 x 10^4 CFU (Cohort 1, n=25), 2.5 x 10^5 CFU (Cohort 2, n=25), and either 2.5 x 10^6 CFU (n=25) or 2.5 x 10^5 CFU (n=13) plus 2.5 x 10^4 CFU (n=12) (Cohort 3) (24 BCG; 75 MTBVAC).

Vaccination of newborns will be staggered to allow gradual evaluation of safety and reactogenicity at each escalation of MTBVAC dose. Progression from the 2.5×10^5 to the 2.5×10^6 CFU dose level, for which safety has not yet been demonstrated, will require that all of the following criteria have been met: (1) no pre-defined pausing rules have been observed at lower MTBVAC dose levels in this trial; (2) favourable review of day 28 safety data of all lower MTBVAC dose groups by the Data Safety Monitoring Board (DSMB); (3) favourable review of safety data from the current pilot Phase 1b infant trial by the DSMB; and (4) favourable review of day 28 safety data for the 2.5×10^6 CFU dose level in QFT negative adults in the parallel adult trial by the DSMB. In the event that any one of these safety criteria are not met, Cohorts 1 and 2 will be expanded so that 33 additional neonates will randomly allocated to receive the 2.5×10^4 CFU dose (n=12), the 2.5×10^5 CFU dose (n=13) or BCG (n=8) by default. If there is a delay in adult data, dose escalation in infants will either be delayed, or Cohorts 1 and 2 be expanded as mentioned above.

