7 STUDY INTERVENTION/INVESTIGATIONAL PRODUCT

7.1 Study Product Description

7.1.1 Acquisition

MTBVAC (live attenuated derivative of *Mtb*) was developed at University of Zaragoza, Spain, by [name], and licensed to Biofabri, SL. MTBVAC and excipient solution for dilution will be supplied by Biofabri.

BCG vaccine (BCG SSI, a WHO pre-qualified BCG vaccine)

Formulation, Packaging, and Labeling

The composition of MTBVAC is shown in Table 7-1. Refer to the most recent version of the Vaccine Management Manual for further details on formulation and packaging for MTBVAC.

Table 7-1 Composition of MTBVAC Study Vaccine

Vaccine Dose ^a	Formulation (approximately per standard dose)	Presentation	Volume
MTBVAC 2.5 x 10 ⁵	1.5 – 8.5 x 10⁵ CFU Sucrose Sodium glutamate	Lyophilized pellet in vials (20 doses)	0.05 mL/dose ^b
MTBVAC 2.5 x 10 ⁶	1.5 – 8.5 x 10 ⁶ CFU Sucrose Sodium glutamate	Lyophilized pellet in vials (20 doses)	0.05 mL/dose ^b

a MTBVAC 2.5×10^4 dose to be prepared by dilution with excipient solution of 2.5×10^5 formulation.

Refer to the package insert for formulation details of BCG.

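### The adult-data condition for the top newborn dose names 2.5 x 10⁶ CFU, a level the adult trial does not include; Section 5 sets the same condition at 5 x 10⁶ CFU

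*Combined protocol and SAP*

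**What the plan says.** Section 3.3.1 sets four criteria, all of which must be met before moving from 2.5 x 10⁵ to 2.5 x 10⁶ CFU in newborns. The fourth is "favourable review of day 28 safety data for the 2.5 x 10⁶ CFU dose level in QFT negative adults", taken from the parallel adult trial and reviewed by the DSMB. Section 6.3.1 repeats the list with the same 2.5 x 10⁶ figure, for the "CFU dose level in QFT negative adults in the parallel adult trial by the DSMB".

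Section 5 describes that adult trial. Its doses "are being tested in a parallel trial among M. tuberculosis infected and uninfected South African adults", at four levels: 5 x 10³, 5 x 10⁴, 5 x 10⁵ and 5 x 10⁶ CFU. The adult part of the condition for the top newborn dose is set there at the "5 x 10⁶ CFU MTBVAC dose in QFT negative adults". The requirement as a whole is worded as "an acceptable safety profile (as defined in Section 3.3.1), both for all lower MTBVAC doses in infants", with the adult dose added after it.

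If any criterion fails, Section 3.3.1 replaces the top-dose cohort with 33 further infants: 12 at 2.5 x 10⁴ CFU, 13 at 2.5 x 10⁵ CFU and 8 on BCG. For late adult data it says: "If there is a delay in adult data, dose escalation in infants will either be delayed, or Cohorts 1 and 2 be expanded".

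**The concern.** This is an operative rule, not background text. It decides whether newborns receive a dose whose safety in infants was unknown when the protocol was written. The two sections that list the criteria name an adult dose that the adult trial, as described, does not give. Section 5 names a dose that it does give.

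The cross-references do not settle the matter. Section 5 cites Section 3.3.1 as the definition, which leads to 2.5 x 10⁶. Section 12.3.1 says escalation follows Section 5, which leads to 5 x 10⁶. Nothing says which prevails.

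The record of the decision is at stake. If the top dose is given on adult data at 5 x 10⁶ CFU, an inspector or ethics committee reading Section 3.3.1 or 6.3.1 would find criterion 4 unmet as written. If the criterion is applied as written, the top dose is withheld for a reason the authors probably did not intend.

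**Working it through.** The check is a comparison of text with a little arithmetic. No sample size, power or error rate is involved.

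**Adult dose named in each place**

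| Section | Adult dose | Role |
|---|---|---|
| 3.3.1 | 2.5 x 10⁶ CFU | criterion 4 |
| 6.3.1 | 2.5 x 10⁶ CFU | criterion 4, repeated |
| 5 | 5 x 10³, 5 x 10⁴, 5 x 10⁵, 5 x 10⁶ CFU | doses of the parallel adult trial |
| 5 | 5 x 10⁶ CFU | condition for the top newborn dose |

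Each figure appears twice and the difference is in the leading number, so a one-off slip or a damaged exponent does not explain it.

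**Does any listed adult level equal 2.5 x 10⁶ CFU?** Ratio of each level to 2.5 x 10⁶:

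- 5 x 10³ / 2.5 x 10⁶ = 0.002
- 5 x 10⁴ / 2.5 x 10⁶ = 0.02
- 5 x 10⁵ / 2.5 x 10⁶ = 0.2
- 5 x 10⁶ / 2.5 x 10⁶ = 2

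None equals 1. The nearest is 2-fold higher: log10(2) = 0.30.

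**Size of the gap against product variation.** Table 7-1 gives 1.5 to 8.5 x 10⁶ CFU for the nominal 2.5 x 10⁶ dose, a width of 8.5 / 1.5 = 5.67-fold. The 2-fold gap is smaller than that, and 5 x 10⁶ lies inside the range.

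**Could 2.5 x 10⁶ be a real adult level from elsewhere?** Section 3.2 shows adults dosed in both series. Phase 1a used 5 x 10³ to 5 x 10⁵ CFU. The Phase 1b newborn study was "preceded by a pilot safety group of adults, previously BCG-vaccinated at birth, who received MTBVAC" at 2.5 x 10⁵ CFU. A 2.5-series adult dose is therefore not absurd on its face, but that group is in a different trial and is 10-fold below the level at issue, so it cannot satisfy criterion 4.

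**Could equal concentration explain it?** Newborns receive 0.05 mL (Section 7.2), so 2.5 x 10⁶ CFU is 2.5 x 10⁶ / 0.05 = 5 x 10⁷ CFU/mL. The adult volume is not given. At an assumed 0.1 mL, 5 x 10⁶ CFU is also 5 x 10⁷ CFU/mL; at an assumed 0.05 mL it is 1 x 10⁸ CFU/mL, twice as high. Even in the first case the stated CFU per dose would differ, and the protocol offers no such rationale.

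**What each reading does to the trial**

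| Reading | 2.5 x 10⁴ | 2.5 x 10⁵ | 2.5 x 10⁶ | BCG | Total |
|---|---|---|---|---|---|
| Section 5 (criterion 4 can be met) | 25 | 25 | 25 | 24 | 99 |
| Literal 3.3.1 / 6.3.1 (cannot be met) | 25 + 12 = 37 | 25 + 13 = 38 | 0 | 24 | 99 |

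The first row assumes that the other three criteria are met.

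**The case against.** The strongest reply is that this is editorial. Section 5 names the trial, the population and the dose, and only one listed adult level could support the top newborn dose. A DSMB asked for top-dose data in QFT-negative adults has one dataset to look at. Neither reading lowers protection: the literal one withholds the top dose, and the Section 5 one relies on adult data at twice the nominal newborn dose. Criteria 1 to 3 are untouched. Section 5 also bases the Cohort 3 dose on the latest safety and immunogenicity data from all MTBVAC trials. The DSMB works under a charter that is not in these documents and may already carry the right figure. Finally, this is Version 4.0 of April 2021, while the adult data were expected around the turn of 2018 to 2019, so the decision may already have been taken.

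Most of that stands, and it limits the severity. The intended figure is recoverable and no harm to participants follows. It does not remove the fault. The two sections that list the criteria carry a figure that the adult trial cannot supply, and Section 5 defers to one of them. Whether Cohort 3 had been dosed by Version 4.0 is not stated.

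**Conclusion.** The point holds. Criterion 4 in Sections 3.3.1 and 6.3.1 names an adult dose that is not among the four listed for the adult trial, and it conflicts with Section 5 by a factor of 2. It should be fixed because it sits in the rule for first use of the highest newborn dose and, taken literally, changes which doses Cohort 3 receives. It does not weaken the safety check, and no endpoint or analysis method depends on it. The conclusion assumes that Section 5 reports the adult trial's doses correctly and completely; no adult-trial document is available to confirm that. Confidence in the inconsistency is high. That 5 x 10⁶ is the intended figure is an inference from Section 5.

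**What to change.** In Sections 3.3.1 and 6.3.1, change the adult dose in criterion 4 to 5 x 10⁶ CFU, matching Section 5. If 2.5 x 10⁶ CFU is really meant, state why adult and newborn doses are treated as equivalent and correct Section 5. Confirm that the DSMB charter uses the same figure. If Cohort 3 has already been dosed, add a file note recording which adult dose level the DSMB reviewed.

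The edit is one figure in two places, with no change to participants, procedures or analyses. The administrative cost is larger than the edit. Section 15.1 requires ethics and regulatory approval of protocol changes before they take effect, and Section 15.2 eases prior ethics approval for purely logistical or administrative changes, which an escalation criterion may not be. It can go into the next amendment unless the escalation decision is still open, in which case it should be made first.
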